## 15.5. Pharmacokinetics Analysis

PK parameters, including but not limited to AUC, maximum concentration ( $C_{max}$ ), time to maximum concentration ( $t_{max}$ ), elimination half-life ( $t_{1/2}$ ), apparent clearance (CL/F), and volume of distribution ( $V_z/F$ ) will be assessed in Part 1 and Part 2. Additional analyses will be performed to assess possible drug-drug interactions, exposure/response, and exposure/toxicity relationships. For all PK analyses, the PK population will be used.

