- Concomitant medications taken within 28 days prior to study day 1 will be collected.
- Adverse events will be collected after the first dose administration. Non-serious AEs prior to dosing on study day 1 will be collected as medical history.
- PK blood sample collection should be performed pre-dose for dalantercept/placebo and axitinib at C1D1, C2D1 and C3D1. C3D1
- If the patient has stable or responding disease at the end of 6 cycles of treatment, repeat the procedures performed for cycles 5 and 6 until the patient is taken off study (C7D1=C5D1, C8D1=C6D1, etc.). NOTE: After C5, ADA, urinalysis, thyroid function and PD biomarkers only need to be repeated once every 4 cycles (C9D1, C13D1, etc).
- Patients who terminate from the study should complete the final visit. The final visit should occur approximately 30 days after the last dose of dalantercept/placebo  $\pm$  10 days. The tumor response assessment scans at the final visit should only be performed to assess progression if progression has not already been confirmed by a previous tumor response assessment scan.
- If the patient has a positive ADA result at their last assessment, the patient may be asked to return approximately every three months for additional testing, until a negative result is obtained or the result is considered stabilized.
- All patients should be contacted every 3 months ( $\pm$  2 weeks) from the date of the final visit for survival. Patients will also be asked to return to the clinic approximately once every 3 months for tumor response assessment scans if progression of disease has not previously been documented. Patients that discontinue study treatment and initiate a new therapy or continue on axitinib alone, prior to documented radiographic disease progression are not required to return to the clinic every 3 months for tumor response assessment scans.

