#### **Part 2 (randomized, double-blind, placebo-controlled):**

Based upon recommendations from the SRT and per sponsor decision, 130 patients will be enrolled and randomized in a 1:1 configuration to receive either the recommended Phase 2 dose level for Part 2 of dalantercept as identified in Part 1, (n=65) or placebo (n=65) plus axitinib. Patients will receive dalantercept/placebo once every 3 weeks by SC injection and continuous dosing of axitinib at a starting dose of 5 mg PO BID, with dose modification of each drug as indicated per protocol or prescribing information, respectively. Treatment will be discontinued for progression of disease, as defined by RECIST (version 1.1, [Appendix 1](#)) or discontinuation of either dalantercept/placebo or axitinib.

All patients will undergo a final visit approximately 1 month following their last dose of dalantercept or placebo and begin follow-up for progression of disease and patient survival. If a patient has a positive ADA result at the last visit, the patient may be asked to return for additional ADA testing every three months, until a negative result is obtained or the result is considered to be stabilized.

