### **10.3. Randomization and Blinding**

**Part 1:** This is an open-label dose escalation that does not require randomization.

**Part 2:** Patients will be randomized to receive 0.9 mg/kg of dalantercept or placebo plus axitinib 5 mg PO BID. Randomization assignments will be generated through a computerized system, provided by an Interactive Web Response System (IWRS). Patients who have signed informed consent and met all eligibility criteria will be stratified according to prior mTOR therapy and prior immune therapies. Patients will then be randomly assigned to dalantercept or placebo plus axitinib within each stratum.

Only the pharmacist or his/her designee who prepares the study drug (dalantercept or placebo) and an unblinded clinical research associate at the CRO will be unblinded to the patient treatment assignments. All other study personnel, including but not limited to Investigators, study coordinators, nursing staff, clinical monitors, the Sponsor, and the Sponsor's representatives, will remain blinded to the study treatment assignments.

In the event of a medical emergency for an individual patient in which knowledge of the study drug is critical to the patient's medical management, the investigator may break the blind for that patient. However, prior to breaking the blind, every effort must be made by the investigator to first discuss the need to break the blind with the medical monitor. Further, it must be determined by the investigator that breaking the treatment blind is necessary information for the medical management of that patient. If the blind is broken, investigator discretion, in consultation with the medical monitor as needed, should be used to determine if the patient should continue on treatment or be discontinued from the study.

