#### **11.3.1. Pharmacokinetic Assessments**

Blood will be collected as outlined in the Schedule of Events ([Section 2](#)) to assess serum levels of dalantercept and axitinib.

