### **12.2. Dosing Days and Interim Visits**

- All screening and study day 1 procedure results required to confirm eligibility must be obtained and reviewed prior to study drug administration. Patient eligibility for inclusion/exclusion criteria must be confirmed from these results, as applicable. Ideally, patients should be randomized within 48 hours of C1D1.
- Baseline hematology, chemistry, and urinalysis results must be reviewed prior to dosing on C1D1 but may be collected up to 72 hours prior to dosing. Baseline thyroid function may also be collected up to 72 hours prior to dosing. Therefore if the screening visit occurs within 72 hours of study day 1, the hematology, chemistry, thyroid function and urinalysis testing do not need to be repeated.
- Any non-serious AEs that occur prior to dosing in cycle 1 should be recorded in the medical history section of the CRF.
- All AEs that occur after dosing in cycle 1 should be recorded in the AE page of the CRF.

- On subsequent dosing days, all AEs and abnormal laboratory or other findings that might require modification of dosing (see [Section 10.6](#)) should be reviewed prior to dosing to ensure that the patient is still eligible to receive additional doses of dalantercept/placebo. Please note that there is an extended window of up to 5 days for the ECHO and tumor response assessment scan, when required.
- PK blood sample collection should be performed pre-dose for dalantercept/placebo and axitinib at C1D1, C2D1 and C3D1.
- Tumor response assessment scans should be performed every 6 weeks regardless of dalantercept/placebo or axitinib dosing delays through C15. After C15 tumor response assessment scans should be performed every 12 weeks regardless of dalantercept/placebo or axitinib dosing delays (e.g. C19D1, C23D1, etc.).
- The schedule of events outlines procedures through C6D1. If patients have stable or responding disease and are able to continue beyond 6 cycles of treatment, the procedures outlined for cycle 5 and 6 should be repeated until the patient comes off study (i.e. C7D1=C5D1, C8D1=C6D1, etc.). The only exception is that after cycle 5, ADA, urinalysis, thyroid function and PD biomarkers are required once every 4 cycles instead of once every 2 cycles (i.e., C9D1, C13D1, etc.).

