#### Analysis Populations:

The **All Treated (AT) Population** includes all patients who received any study drug. The AT is the population that will be used when performing the primary analysis of the primary endpoint and all safety analyses. The AT population will be analyzed according to treatment received.

The **Full Analysis Set (FAS)** includes all randomized patients. The intent-to-treat principle will be used for this study population. The FAS will be used in secondary analyses of the primary endpoint.

The **Pharmacokinetics (PK) population** will consist of all patients who received at least 1 dose of dalantercept and axitinib and have sufficient PK samples collected and assayed.

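### The PK population in section 15.5 shuts out the placebo-plus-axitinib arm, the only randomized, dalantercept-free comparator for the effect of dalantercept on axitinib trough

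*Combined protocol and SAP*

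**What the plan says.** Section 15.5 lists PK parameters for Part 1 and Part 2 and adds: "Additional analyses will be performed to assess possible drug-drug interactions". It closes with "For all PK analyses, the PK population will be used", with no exception for any analyte or question.

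The PK population, defined in the synopsis and again in section 15, is "all patients who received at least 1 dose of dalantercept and axitinib and have sufficient PK samples collected and assayed".

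Part 2 randomizes 1:1 (section 9.1: "n=65) or placebo (n=65) plus axitinib"). Section 10.3 confirms the contrast: "Patients will be randomized to receive 0.9 mg/kg of dalantercept or placebo plus axitinib 5 mg PO BID".

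Sampling is the same in both arms. Section 12.2 says: "PK blood sample collection should be performed pre-dose for dalantercept/placebo and axitinib at C1D1, C2D1 and C3D1". Footnote 15 of the Schedule of Events gives the same three times, followed by a stray visit label. Section 11.3.1 refers back to that schedule: "Blood will be collected as outlined in the Schedule of Events".

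**The concern.** An interaction has two directions. To learn whether axitinib changes dalantercept, one needs patients who received dalantercept, and the PK population serves. To learn whether dalantercept changes axitinib, one needs axitinib concentrations with and without dalantercept. The PK population keeps only the first half of that contrast.

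The trial randomizes patients to the missing half and schedules their blood samples. The population rule then prevents those samples from being used in the analysis they suit best. Any statement about dalantercept and axitinib concentrations would have to rest on non-randomized comparisons among patients who all received dalantercept.

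**Working it through.** The protocol gives no sample size, power or precision for any PK analysis, so there is no planned figure to reproduce. The check is mainly one of logic.

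**1. Who qualifies.** Membership needs a dose of dalantercept, a dose of axitinib and sufficient samples. Placebo patients fail the first condition. The planned loss from axitinib analyses is 65 / 130 = 50% of Part 2. The axitinib comparison has up to 65 dalantercept patients and 0 placebo patients, so no between-arm ratio can be formed.

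**2. Can patients be their own controls?** No.
- The Schedule of Events shows continuous axitinib dosing and no axitinib-alone lead-in.
- The C1D1 sample is taken before dosing, so it contains neither study drug.
- C2D1 and C3D1 both follow dalantercept in that arm.
- Section 12.2.2 recognizes that some patients continue on axitinib alone after stopping study treatment, but no PK sample is scheduled then.

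**3. What remains under the rule.**
- Comparison across Part 1 dalantercept dose levels: not randomized, and no zero-dose group.
- Paired dalantercept and axitinib troughs within the Part 2 dalantercept arm. At C2D1 every patient has had one dose, assigned at 0.9 mg/kg, so the spread in dalantercept trough is between-patient variation. Dose reductions add spread only from C3D1, and they follow adverse events.

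**4. Which visit suits the comparison.** With visit windows counted from the previous dose, C2D1 falls 21 ± 2 = 19 to 23 days after the first dose (axitinib assumed to start on study day 1). Section 10.6.2 allows axitinib increases only after four consecutive weeks (28 days), so an on-schedule C2D1 sample precedes any permitted increase. Reductions and interruptions can already have occurred. A dalantercept/placebo delay of more than 7 days moves C2D1 past day 28 (21 + 7 = 28). The 3-week maximum delay puts it at 21 + 21 = 42 days. C3D1, at about 42 days on schedule, is later than 28 days in any case.

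**5. Illustrative precision.** The documents give no between-patient CV for axitinib trough. I assume 60% to 120%. The 95% interval for the geometric mean ratio is the estimate multiplied and divided by

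exp( t(0.975, 2n−2) × s × √(2/n) ), with s = √ln(1 + CV²).

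| Assumed CV | s | n = 65 per arm | n = 45 per arm (assumed usable) |
|---|---|---|---|
| 60% | 0.555 | 1.21 | 1.26 |
| 120% | 0.944 | 1.39 | 1.49 |

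This shows only that the comparison could be informative. It does not measure the size of the flaw.

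**6. Side check on the parameter list.** Each patient has two informative pre-dose samples per analyte. In a one-compartment model with rapid absorption, the dalantercept trough ratio C3D1/C2D1 is 1 + exp(−21 × ln 2 / t½). That gives 1.23 at 10 days and 1.45 at 18 days, the ends of the half-life ranges in sections 7.3 (10–15 days) and 9.2.3 (14–18 days). Troughs therefore carry some information on half-life. They say little about the peak. With half-life fixed and first-order absorption, moving tmax from 4 to 7 days (the stated range) changes that ratio by at most 0.005. The same move changes Cmax relative to the C2D1 trough by 1.20- to 1.47-fold and AUC(0–21d) by 1.13- to 1.29-fold.

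**The case against.** **The definition might be read loosely, so that placebo counts.** This is hard to sustain. Where the protocol means both arms it writes dalantercept/placebo or dalantercept or placebo, as in sections 10.6.1 and 12.2. If the looser reading is intended, the wording still needs correcting.

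**The SAP can repair it.** Section 15.1 defers analysis detail to a separate SAP, and section 15.6 lets that SAP depart from the protocol. Neither it nor the Study Reference Guide is available here. This stands as a limit: an axitinib set may already exist there. It would, however, be a departure from an explicit rule in the protocol.

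**A pre-dose sample is not exposure.** This stands in full. Axitinib is taken twice daily and largely at home, so the arm comparison can show a difference in trough only.

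**Importance is low.** This also stands. Section 8 lists a PK objective for Part 1 only, and the interaction analyses carry no hypothesis, endpoint or power claim.

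**A stronger reading of section 15.5.** A reader might infer that its parameter list is an error because pre-dose samples cannot yield AUC, Cmax, tmax, CL/F or Vz/F. The documents do not support that. The section says only that these will be assessed, which leaves room for model-based estimation, and the two troughs do inform half-life. An unnamed model is detail left to documents not seen.

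**Conclusion.** The exclusion follows directly from the definition and the all-analyses rule. As written, the plan cannot use the only dalantercept-free, randomized comparator for the effect of dalantercept on axitinib trough concentration: 65 of 130 planned Part 2 patients, whose samples are already scheduled.

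The finding goes no further than that. A reader might infer that the trial cannot study interactions at all. It can: the effect of axitinib on dalantercept is untouched by this exclusion, and non-randomized looks at the other direction remain possible. Nor would readmitting the placebo arm settle axitinib AUC or Cmax.

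Severity is minor, and the primary PFS analysis is unaffected. The conclusion assumes that the protocol rule is followed as worded and that the unseen SAP does not override it. The precision figures rest on assumed CVs and assumed usable numbers.

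As a side note, the visible schedule gives troughs only. AUC, Cmax, tmax, CL/F and Vz/F would need a model or richer sampling to be named in the SAP or Study Reference Guide.

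**What to change.** 1. **Define the PK population by analyte.** For dalantercept, keep the present definition. For axitinib, include all patients in either arm with at least 1 axitinib dose and at least 1 usable post-baseline axitinib sample. Amend section 15.5 so that each PK analysis uses the set for its analyte.
2. **Name the comparison.** For the effect of dalantercept on axitinib, compare pre-dose axitinib concentrations at C2D1 between the randomized arms as a geometric mean ratio with a confidence interval. State that the ratio describes trough, not AUC or Cmax, and is net of any axitinib dose changes. Also state that it covers only patients with a usable sample, so loss before C2D1 should be reported by arm.
3. **Add a dose-normalized version as supportive only**, because the axitinib dose at that visit is determined after randomization.
4. **In the SAP or Study Reference Guide**, name the model or sampling behind any parameter other than trough.

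The cost is revised wording, axitinib assays of placebo-arm samples already scheduled, and a small amount of analysis. No additional blood draw is needed. Section 15.6 allows the change to be recorded in the SAP before database lock.

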## 15.6. Deviation from Original Analysis Plan

A formal SAP for the analysis and presentation of data from this study will be prepared before database lock. Deviations from the statistical analyses outlined in this protocol will be indicated in this plan; any further modifications will be noted in the final clinical study report.

## **16. SOURCE DOCUMENTATION AND INVESTIGATOR FILES**

### **16.1. Study Monitoring**

The CRA will arrange to visit the investigator sites at regular intervals during the study. The monitoring visits must be conducted according to the applicable ICH and GCP guidelines to ensure protocol adherence, quality of data, drug accountability, compliance with regulatory requirements, and continued adequacy of the investigational sites and their facilities. During these visits, CRFs and other data related to the study will be reviewed and any discrepancies or omissions will be resolved. The CRA will be given access to study relevant source documents (including medical records) for purposes of source data verification (SDV).

### **16.2. Audits and Inspections**

The investigators and clinical sites will permit trial-related monitoring, audits, IRB review, and regulatory inspections as requested by FDA and the sponsor or designee. In addition to CRFs, the clinical site will permit direct access to source data/documents (i.e., original medical records, laboratory reports, hospital documents, progress reports, signed ICFs, etc.). During and/or after completion of the study, quality assurance officers named by the sponsor or the regulatory authorities may wish to perform on-site audits. The investigator is expected to cooperate with any audit and provide assistance and documentation (including source data) as requested.

## **17. QUALITY CONTROL AND QUALITY ASSURANCE**

### **17.1. Data Quality Control and Quality Assurance**

#### **17.1.1. Investigator Responsibility**

The investigator is responsible for ensuring the study is conducted according to the protocol, CFRs, GCP, and applicable regulatory requirements. The investigator's responsibilities are outlined in these documents and must include the responsibility to obtain a signed informed consent prior to patient participation in the study.

#### **17.1.2. Protocol Modifications**

The investigator should not modify the protocol without agreement from the sponsor and prior review or approval by the IRB, unless an emergency situation requires protocol modification to ensure the safety of patients. Any deviations from the protocol should be documented by the investigator or designee.

## **18. CONFIDENTIALITY**

To maintain patient privacy, all CRFs, study drug accountability records, study reports and communications will identify the patient by the assigned patient identification number. The investigator will grant monitor(s) and auditor(s) from the sponsor or designee and regulatory authorities access to the patient's original medical records for verification of data gathered on the CRFs and to audit the data collection process. The patient's confidentiality will be maintained and will not be made publicly available. The patient's medical information will only be released to the extent permitted by the applicable laws and regulations.

All information regarding the investigational product supplied by the sponsor to the investigator is privileged and confidential information. The investigator agrees to use this information to accomplish the study and will not use it for other purposes without consent from the sponsor. It is understood that there is an obligation to provide the sponsor with complete data obtained during the study. The information obtained from the clinical study will be used towards the development of the investigational product and may be disclosed to regulatory authorities, other investigators, corporate partners, or consultants as required.

## **19. PUBLICATION POLICY**

All information concerning dalantercept is considered confidential and shall remain the sole property of the sponsor. The investigator agrees to use this information only in conducting the study and shall not use it for any other purposes without the sponsor's written approval. The investigator agrees not to disclose the sponsor's confidential information to anyone except to persons involved in the study that need such information to assist in conducting the study, and then only on like terms of confidentiality and non-use.

It is understood by the investigator that the information developed from this clinical study will be used by the sponsor in connection with the development of dalantercept, and therefore may be disclosed as required to regulatory agencies. To allow for the use of the information derived from clinical studies, it is understood that there is an obligation to provide the sponsor with complete test results and all data developed in the study.

No publication or disclosure of study results will be permitted except as specified in a separate, written, agreement between the sponsor and the investigator.

## **20. PROTOCOL AMENDMENTS**

Protocol amendments that impact patient safety, change the scope of the investigation, or affect the scientific quality of the study must be approved by the IRB and submitted to the appropriate regulatory authorities before implementation.

In the event that the protocol needs to be modified immediately to eliminate an apparent hazard to a patient, the sponsor will implement the protocol change and subsequently amend the protocol and notify the regulatory authorities and/or the IRB, as appropriate.

## **21. DATA HANDLING AND RECORDKEEPING**

### **21.1. Case Report Form Completion**

Case report forms will be completed for each enrolled patient. It is the investigator's responsibility to ensure the accuracy, completeness, and timeliness of the data reported in the patient's CRF. Source documentation supporting the CRF data should indicate the patient's participation in the study and should document the dates and details of study procedures, AEs, and patient status.

Investigators will maintain copies of the CRFs at the clinical site. For patients who discontinue or terminate from the study, the CRFs will be completed as much as possible, and the reason for the discontinuation or termination clearly and concisely specified on the appropriate CRF.

